Study Protocol

Intraoperative Pain During Carpal Tunnel Release: WALANT vs Local Anesthesia and Tourniquet – A Randomized Controlled Trial

1. Administrative information

- **Protocol Version:** 1.0 (Final), dated 10 October 2024.
- **Principal Investigator (PI):**
 - [name] [name], PhD
 - Associate Professor of Orthopedic Surgery
 - Faculty of Medicine, Misr University for Science and Technology, Giza, Egypt
- **Co-Investigators:**
 - [name] [name], PhD – Assistant Professor of Neurosurgery, Al-Azhar University, Cairo, Egypt
 - Others as per authorship list ([name], [name], [name]).
- **Study Sites:**
 - Site 1: Department of Orthopedic Surgery, tertiary university hospital, Giza, Egypt.
 - Site 2: Department of Neurosurgery, tertiary university hospital, Cairo, Egypt.
- **Regulatory / Ethics Approvals:**
 - Approved by institutional review board/ethics committee at participating centers prior to enrollment.
 - Conducted according to the Declaration of Helsinki and CONSORT 2025 RCT reporting guidance.
- **Funding:**
 - No external funding.

2. Background and rationale

Carpal tunnel decompression (CTD) is one of the most common hand procedures, with several anesthetic options including local anesthesia with pneumatic tourniquet (LA-T), regional block, and general anesthesia. Tourniquet use can cause significant pain, anxiety, and potential complications without proven long-term functional benefit.

Wide-awake local anesthesia no tourniquet (WALANT) uses lidocaine with epinephrine to achieve field anesthesia and vasoconstriction, avoiding tourniquet and sedation, while allowing intraoperative functional assessment and potentially reducing costs and turnaround time. Prior RCTs and observational studies suggest lower perioperative pain and similar complication rates with WALANT, but many are limited by small sample size, non-blinded designs, and single-surgeon experience.

This trial was designed as a multicenter, prospective, double-blinded randomized controlled study to provide high-quality evidence comparing WALANT versus LA-T for intraoperative pain and related outcomes in CTD.

3. Objectives and hypotheses

Primary Objective

To compare intraoperative pain during open carpal tunnel decompression performed under WALANT versus LA-T in adult patients with carpal tunnel syndrome.

Secondary Objectives

- To compare pain during local anesthetic infiltration between WALANT and LA-T.
- To assess tourniquet-specific pain in the LA-T group.
- To compare operative time between groups.

- To compare patient satisfaction with the operating-room experience.
- To describe intraoperative complications in each group.

Primary Hypothesis

WALANT will result in significantly lower overall intraoperative pain (VAS) than LA-T.

Secondary Hypotheses

- Infiltration pain will be similar between WALANT and LA-T.
- Tourniquet pain will contribute to higher intraoperative pain in LA-T.
- WALANT will shorten operative time compared with LA-T.
- Patient satisfaction will be high and not inferior in WALANT compared with LA-T.

4. Study design

Prospective, multicenter, double-blinded, randomized controlled trial with two parallel arms (1:1 allocation). Patients were randomized to WALANT or LA-T and followed through the perioperative period until early postoperative assessment.

- **Study Type:** Interventional, treatment.
- **Interventional Model:** Parallel assignment, two arms.
- **Masking:**
 - Patients and outcome assessors: blinded to group allocation.
 - Surgeons and anesthetic personnel: aware of technique for safety; allocation concealed until after consent and randomization.

5. Study setting and timeline

- **Sites:**
 - Tertiary academic orthopedic and neurosurgical departments in Giza and Cairo, Egypt.
- **Study Period:**
 - Enrollment and follow-up from December 2024 to December 2025.

6. Eligibility criteria

Inclusion Criteria

- Age ≥ 18 years.
- Clinical diagnosis of carpal tunnel syndrome confirmed by nerve conduction and electromyographic studies.
- Candidate for surgical treatment with open carpal tunnel decompression.
- American Society of Anesthesiologists (ASA) physical status I or II.
- Ability to provide written informed consent.

Exclusion Criteria

- Surgery-related anxiety requiring sedation or general anesthesia.
- Known contraindication or allergy to lidocaine or epinephrine.

- Active local or systemic infection at the surgical site.
- ASA physical status III or higher.
- Pregnancy or breastfeeding.
- Inability to understand or complete pain and satisfaction scales, or to provide informed consent.

7. Interventions

Arm A – WALANT

- 20 mL of 1% lidocaine (200 mg) with epinephrine 1:100,000, buffered with 8.4% sodium bicarbonate (10:1 ratio).
- Infiltrated into the operative field approximately 20 minutes before incision in a preoperative area.
- No tourniquet used.
- Mini-open carpal tunnel release through a 2–3 cm incision in a minor procedure room, under full aseptic technique; hemostasis via epinephrine-induced vasoconstriction and meticulous technique.

Arm B – Local Anesthesia With Tourniquet (LA-T)

- 20 mL of 1% lidocaine (200 mg) buffered identically but without epinephrine.
- Infiltrated approximately 5 minutes before incision in the operating room.
- A blood-pressure cuff tourniquet placed above the elbow (no exsanguination), inflated to 100 mmHg above systolic pressure after arm elevation and draping, released after skin closure.
- Mini-open carpal tunnel release through a 2–3 cm incision under standard aseptic conditions.

Two experienced surgeons (orthopedic hand consultant and neurosurgery peripheral nerve specialist) performed all procedures; each performed approximately 50 cases.

8. Outcomes

Primary Outcome

- Overall intraoperative pain (VAS 0–10): patient's rating of pain during the entire surgery, assessed immediately after surgery by a blinded assessor.

Secondary Outcomes

- Infiltration pain (VAS 0–10): pain during local anesthetic injection.
- Tourniquet pain (VAS 0–10): tourniquet-specific pain in LA-T group.
- Operative time (minutes): from skin incision to completion of skin closure.
- Patient satisfaction (0–10 scale): global satisfaction with the operating-room experience.
- Intraoperative complications: bleeding requiring intervention, nerve injury, or other deviations from normal course.

Demographics: age, sex, BMI, ASA class, CTS-6 severity score.

9. Sample size

A target sample of 100 patients (50 per arm) was chosen based on feasibility at the two centers and expected medium effect size in intraoperative pain VAS. Post-hoc analysis showed that with 50 participants per group and the observed

effect size (Cohen's $d \approx 0.75$), power was approximately 94% (two-sided $\alpha = 0.05$) to detect the group difference in intraoperative pain.

10. Randomization and allocation concealment

- Simple computerized randomization with 1:1 allocation to WALANT or LA-T.
- Randomization list held by an investigator ([name]) not involved in surgery or postoperative assessment.
- On the day of surgery, the investigator informed the operating surgeon of the assigned technique after consent, maintaining concealment before enrollment.

11. Blinding

- Patients were not explicitly told which anesthetic technique they received.
- Outcome assessors (who collected VAS and satisfaction scores) were independent and blinded to group assignment.
- Surgical team necessarily aware of technique; however, standardized perioperative communication and identical questionnaires minimized performance bias.

12. Data collection and management

- Standardized questionnaire completed postoperatively by the patient and a blinded assessor captured VAS scores, satisfaction, and complications.
- Operative time and tourniquet parameters abstracted from operative notes.
- Data were entered into a secure, password-protected electronic spreadsheet; quality checks performed for range and consistency.

13. Statistical considerations

See separate SAP (Section B). Briefly, continuous variables were summarized as mean \pm SD or median (IQR) depending on distribution; categorical variables as counts and percentages. Intraoperative VAS (primary outcome) was compared using Mann–Whitney U test; subgroup analyses by age, sex, and surgeon were pre-specified.

14. Ethical considerations

- Approved by IRB/ethics committee at participating institutions.
- All participants provided written informed consent before randomization.
- Risks: injection pain, tourniquet discomfort (LA-T), bleeding, infection, nerve injury, allergic reaction, cardiovascular effects of epinephrine; these are standard risks of hand surgery and local anesthesia.
- Benefits: potential for improved intraoperative comfort; contribution to knowledge that may improve anesthetic choices for future patients.
- Confidentiality: data stored with coded IDs; no identifying information in reports or publications.

B. Statistical Analysis Plan (SAP)

Study: WALANT vs Local Anesthesia With Tourniquet for Carpal Tunnel Decompression – Randomized Controlled Trial

1. Objectives and endpoints

Primary Endpoint

- Overall intraoperative pain VAS (0–10).

Secondary Endpoints

- Pain during anesthetic infiltration (VAS 0–10).
- Tourniquet pain in LA-T group (VAS 0–10).
- Operative time (minutes).
- Patient satisfaction score (0–10).
- Intraoperative complications (yes/no; type).

2. Analysis populations

- **Intention-to-Treat (ITT) Population:**
All randomized participants analyzed according to allocated group, regardless of minor protocol deviations, provided primary outcome data are available.
- **Per-Protocol (PP) Population (exploratory):**
Subset excluding major deviations (e.g., cross-over of anesthetic technique, incomplete surgery) if any occurred. Primary inferences will be based on ITT; PP will be supportive.

3. General statistical principles

- Two-sided tests with significance level $\alpha = 0.05$.
- Continuous variables: reported as mean \pm SD if approximately normal, or median (IQR) if skewed.
- Categorical variables: counts and percentages with 95% confidence intervals.
- Normality checked with Shapiro–Wilk test and inspection of histograms.
- Main analyses non-parametric where distribution assumptions are not met; parametric tests may be reported as sensitivity analyses.
- Statistical software: SPSS version 29.

4. Baseline characteristics

Baseline demographics and clinical characteristics (age, sex, BMI, ASA class, CTS-6 score) will be summarized by group using descriptive statistics.

- Continuous variables: compared using independent-samples t-test or Mann–Whitney U test as appropriate.
- Categorical variables: compared using chi-square or Fisher’s exact test as appropriate.
These comparisons are descriptive; no p-value adjustment is planned as they are not hypothesis-driven.

5. Primary outcome analysis

Outcome: Overall intraoperative pain VAS (0–10).

- **Primary analysis method:**
Mann–Whitney U test comparing VAS scores between WALANT and LA-T.
- Effect size:
 - Median difference with 95% CI.
 - Non-parametric effect size measure (e.g., rank-biserial correlation) as reported; you previously used effect size ≈ 0.63 with 95% CI.

- **Sensitivity analysis:**
Independent-samples t-test (parametric), assuming approximate normality, to corroborate non-parametric findings.

No adjustment for multiple testing is applied to the primary endpoint.

6. Secondary outcomes analysis

1. Infiltration pain VAS (0–10)

- Analysis: Mann–Whitney U test comparing WALANT vs LA-T.
- Report: medians (IQR), means (SD), p-value, and effect size.

2. Tourniquet pain VAS (LA-T only)

- Descriptive analysis within LA-T arm: median (IQR), distribution plots.
- No between-group statistical test (not defined in WALANT arm).

3. Operative time (minutes)

- Analysis: Mann–Whitney U test for group comparison.
- Report: median (IQR) per group, p-value, effect size.

4. Patient satisfaction (0–10)

- Analysis: Mann–Whitney U test to compare satisfaction scores between groups.
- Report: median (IQR), p-value, and effect size.

5. Intraoperative complications

- Analysis: counts and proportions in each group; Fisher’s exact or chi-square test if sufficient events.
- Given low expected event counts, analysis is primarily descriptive.

Multiplicity:

Secondary outcomes are interpreted cautiously; no formal adjustment for multiple comparisons. Emphasis remains on the primary outcome.

7. Subgroup analyses

Pre-specified subgroups:

- Age group: <65 vs ≥65 years.
- Sex: male vs female.
- Surgeon: Orthopedic (Surgeon A) vs Neurosurgery (Surgeon B).

For each subgroup:

- Compare intraoperative VAS between WALANT and LA-T using Mann–Whitney U test within strata.
- Test for interaction (e.g., using non-parametric interaction tests or rank-based methods) to assess whether the treatment effect differs by age, sex, or surgeon; manuscript reported non-significant interactions (age p=0.45, sex p=0.82, specialty p=0.76).

Subgroup findings are exploratory and hypothesis-generating.

8. Handling of missing data

- Missing primary outcome data are expected to be rare because VAS is collected immediately postoperatively.
- If isolated missing VAS values occur, primary analysis will be complete-case (excluding those without any intraoperative VAS value). Given small numbers, imputation is unlikely to materially change results.
- If >5% of participants lack primary outcome data, a sensitivity analysis using simple imputation (e.g., median of group) may be explored, but the main report will transparently present complete-case results.

9. Sensitivity and additional analyses

- **Timing of anesthetic administration:**
Exploratory analyses to assess whether variation in injection-to-incision time confounds results; previous sensitivity analysis showed no meaningful pattern.
- **Post-hoc power:**
Based on observed effect (mean 0.80 vs 2.08, pooled SD 1.52), Cohen's $d \approx 0.75$, and $n=50$ per group, post-hoc power $\approx 94\%$ ($\alpha=0.05$).
- **Graphical displays:**
Box plots and distribution plots for VAS scores, operative time, and tourniquet pain; subgroup plots by age, sex, and surgeon.

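### The similarity and non-inferiority hypotheses for infiltration pain and satisfaction have only a test of difference behind them, so a non-significant result cannot support either

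*Combined protocol and SAP*

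**What the plan says.** Among the Secondary Hypotheses in protocol section 3 are "Infiltration pain will be similar between WALANT and LA-T" and "Patient satisfaction will be high and not inferior in WALANT compared with LA-T". The Secondary Objectives in the same section are milder: for both outcomes the aim is only to compare the groups.

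The SAP plans the same kind of test for each:

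- Infiltration pain (SAP 6.1): "Analysis: Mann–Whitney U test comparing WALANT vs LA-T", with "Report: medians (IQR), means (SD), p-value, and effect size".
- Satisfaction (SAP 6.4): "Mann–Whitney U test to compare satisfaction scores between groups", with "Report: median (IQR), p-value, and effect size".

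SAP section 3 makes all tests two-sided at 0.05. For the primary outcome, SAP section 5 asks for a median difference with a 95% CI. Sections 6.1 and 6.4 ask for an effect size, but do not say which measure or whether it carries an interval. No non-inferiority margin, equivalence bound, pair of one-sided tests or confidence-limit rule appears in either document. The *high* part of the satisfaction hypothesis has no threshold. The multiplicity note in SAP section 6 says that secondary outcomes will be read with caution and that the emphasis stays on the primary outcome.

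**The concern.** The null hypothesis of a Mann–Whitney test is no difference between the groups. Failing to reject it means that no difference was detected. It does not show that any difference is small enough to ignore, which is what *similar* and *not inferior* assert. Supporting those claims needs a stated limit on the acceptable difference and an interval compared with that limit. The plan has neither, so if either test is non-significant the matching hypothesis is left undecided.

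Both outcomes bear on how acceptable WALANT is to patients. A statement that the injection hurts no more, or that patients are no less satisfied, could influence practice even if the data were compatible with a difference that matters.

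**Working it through.** **Inputs.** 50 per arm (protocol section 9); two-sided alpha 0.05 (SAP section 3). The documents give no SD, margin or minimal important difference for either score. Results are therefore given in SD units first, then in points for assumed SDs of 1.0 to 2.5. That range includes 1.52, the pooled SD quoted for the primary VAS in SAP section 9.

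**Step 1: the plan's own figure.** The only power figure is about 94%, for the primary outcome at d ≈ 0.75. The noncentral t has noncentrality d × √(n/2) = 0.75 × √25 = 3.75 on 98 df, and gives 96.0%. For the Mann–Whitney test, scale n by its asymptotic relative efficiency of 0.955 under normality: 50 × 0.955 = 47.75, noncentrality 0.75 × √23.875 = 3.66, power 95.2%. With the minimum efficiency of 0.864, power is 93.1%. The stated figure is thus approximately reproduced, and the same method is used below.

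**Step 2: chance of p > 0.05 when a difference exists.** This is 1 − power, with effective n 47.75, 93.5 df and critical value 1.986.

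| True difference | Noncentrality | P(p > 0.05) |
|---|---|---|
| 0.3 SD | 0.3 × 4.886 = 1.47 | 69% |
| 0.4 SD | 0.4 × 4.886 = 1.95 | 51% |
| 0.5 SD | 0.5 × 4.886 = 2.44 | 32% |

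**Step 3: the same in points.**

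| Assumed SD | P(p > 0.05), true 0.5 points | P(p > 0.05), true 1.0 point |
|---|---|---|
| 1.0 | 32% | 0.2% |
| 1.52 | 64% | 11% |
| 2.0 | 77% | 32% |
| 2.5 | 84% | 51% |

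These figures assume roughly normal scores. As a check, Mann–Whitney tests were simulated on scores rounded and limited to 0–10, with SD 1.52 and a 0.5-point shift before limiting (4,000 trials per setting). They were non-significant in 65% to 66% of trials for comparator means of 5, 8.5 and 9, against 64% from the formula. Near the ceiling the realised difference shrinks: to about 0.40 points at a mean of 9.

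**Step 4: what an interval would show.** For a mean difference, the 95% CI half-width is t(0.975, 98) × SD × √(2/50) = 1.984 × 0.2 × SD = 0.397 SD. That is 0.40 points at SD 1.0, 0.60 at 1.52, 0.79 at 2.0 and 0.99 at 2.5.

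**Step 5: the margin that 50 per arm could have supported.** With true difference 0, 80% power and one-sided 0.025, the smallest non-inferiority margin is 0.2 × SD × (1.960 + 0.842) = 0.560 SD, or 0.85 points at SD 1.52. For two one-sided tests at 0.05 each, the smallest equivalence bound is 0.2 × SD × (1.645 + 1.282) = 0.585 SD, or 0.89 points at SD 1.52. At that SD, non-inferiority power is Φ(1.0/0.304 − 1.96) = 91% for a 1.0-point margin and Φ(0.5/0.304 − 1.96) = 38% for a 0.5-point margin. Whether the trial could support such a claim depends on the margin that the plan does not state.

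**The case against.** The strongest reply is that the formal objectives are only to compare, and a test of difference fits that aim. On this reading the hypotheses express expectations, not a non-inferiority or equivalence design. The outcomes are secondary, the SAP promises cautious interpretation, and the undefined effect size may have been meant to carry an interval, as it does for the primary outcome. Much of this is fair, and it limits the weight of the point. It does not remove it: the hypotheses go further than the objectives, the caution is stated under multiplicity and gives no rule for reading a non-significant result, and carrying the interval over to SAP 6.1 and 6.4 is plausible but not written.

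Three stronger readings are tempting, and the documents do not support them:

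- *A non-significant p-value will be counted as support.* Neither document says so. What can be said is that no criterion is offered for concluding similarity, or for concluding non-inferiority short of superiority.
- *The analysis cannot answer either hypothesis.* That ignores significant results. One favouring WALANT on satisfaction supports *not inferior*, and one against WALANT counts against it. A significant difference in infiltration pain counts against *similar*.
- *A real difference would probably be missed.* That holds only below about 0.4 SD. At 0.5 SD the chance of p > 0.05 is 32%, and for a full point at SD 1.52 it is 11%. Without a minimal important difference, the documents cannot show whether 0.3 to 0.4 SD matters to patients.

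**Conclusion.** The point holds, confined to non-significant results. For these two hypotheses the plan has a test of difference and nothing that could turn p > 0.05 into evidence of similarity or non-inferiority. The size of the gap is the 69%, 51% and 32% chance of a non-significant result at true differences of 0.3, 0.4 and 0.5 SD. This rests on 50 analysed per arm and approximately normal scores; any translation into points rests on an assumed SD. The change is worth making but is not critical, since both outcomes are secondary and the primary superiority comparison does not depend on them.

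**What to change.** In SAP 6.1 and 6.4:

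1. Make the Hodges–Lehmann (or mean) difference, WALANT minus LA-T, with its 95% CI the main result. Keep the Mann–Whitney p-value beside it.
2. Leave both hypotheses visible as stated, and disclose that no margin or equivalence bound was pre-specified.
3. State that p > 0.05 shows neither similarity nor non-inferiority, and that neither word will be used in the conclusions on that basis.
4. If a margin is added now, justify it from outside the trial data and label it post hoc, because the SAP already cites observed results (sections 5, 7 and 9). Satisfaction would then be called not inferior only if the lower confidence limit lies above minus the margin, and infiltration pain similar only if the whole interval lies within the bounds. Any rewording of the hypotheses must be disclosed in the same way.

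The cost is a few sentences in the SAP and one interval per endpoint, with no new data. Justifying margins, if that route is taken, is additional work. The downside is weaker secondary claims.

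### Patients are described as blinded, but an awake patient can tell whether an arm cuff was inflated; assessor blinding is claimed without the safeguard it needs

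*Combined protocol and SAP*

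**What the plan says.** Protocol Section 4 describes the design as "Prospective, multicenter, double-blinded, randomized controlled trial with two parallel arms (1:1 allocation" and, under Masking, adds "Patients and outcome assessors: blinded to group allocation". Surgeons and anesthetic personnel are acknowledged to know the technique. Section 2 counts non-blinded designs among the weaknesses of earlier studies, then introduces this trial as double-blinded and able to give high-quality evidence.

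Section 11 gives the means. For patients: "Patients were not explicitly told which anesthetic technique they received". For assessors: they are independent, blinded, and collect the VAS and satisfaction scores. For the surgical team, who know the technique: "standardized perioperative communication and identical questionnaires minimized performance bias".

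Section 7 gives LA-T "A blood-pressure cuff tourniquet placed above the elbow (no exsanguination" in brackets), inflated to 100 mmHg above systolic pressure and released after skin closure. WALANT has no tourniquet. Section 8 makes the patient's own rating of pain over the whole operation the primary outcome, and includes among the secondary outcomes "tourniquet-specific pain in LA-T group". Section 12 describes the instrument: "Standardized questionnaire completed postoperatively by the patient and a blinded assessor captured VAS scores, satisfaction, and complications".

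**The concern.** The claim of patient blinding and the procedures do not fit together. The arms differ by a physical event on the patient's own arm, and the plan describes nothing that hides it. Withholding the name of a technique is non-disclosure; it does not mask what the patient feels.

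This matters because the primary outcome and satisfaction are both subjective ratings given by that patient. A patient who knows which technique was used may rate according to expectation as well as experience, and the comparison then carries both. Readers who take the double-blind label at face value would discount that possibility, and Section 2 invites them to trust this trial more than earlier non-blinded ones for that reason.

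The second strand is the assessor. A tourniquet-pain score exists for one arm only, so whoever collects it learns the arm. If that happens before the primary VAS is recorded, the assessor is no longer blind for the primary outcome.

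**Working it through.** The claim contains no figure to reproduce, so the check sets the passages side by side. A short calculation of scale follows.

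**1. Are patients awake?** Both arms use local anesthesia only (Section 7). Section 2 describes WALANT as avoiding sedation, and Section 6 excludes "Surgery-related anxiety requiring sedation or general anesthesia". No sedation is described in either arm.

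**2. What can an awake patient perceive?**

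| Feature | WALANT | LA-T | Source |
|---|---|---|---|
| Upper-arm cuff | None; no sham described | Inflated to 100 mmHg above systolic until after closure | Section 7 |
| Injection | Preoperative area, about 20 min before incision | Operating room, about 5 min before incision | Section 7 |
| Room for surgery | Minor procedure room | Not named | Section 7 |
| Tourniquet-pain VAS | Not defined | Collected | Section 8; SAP Section 6 |

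The cuff row carries the argument. Asking LA-T patients to score tourniquet pain presupposes that they knew a tourniquet was on. The injection and room rows add little: each patient experiences one arm, so place and waiting time reveal allocation only to someone who knew what the other arm involved.

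**3. What is set against this?** Only non-disclosure (Section 11). No sham, screen or check of blinding success appears, and SAP Section 9 has no analysis that addresses unblinding.

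**4. Can the assessor stay blind?** Section 11 has the blinded assessors collecting VAS scores, and Section 12 puts VAS scores on one questionnaire. Section 12 does not list the tourniquet VAS by name, but it is one of the VAS outcomes in Section 8 and no other route is given for it. (The tourniquet parameters taken from operative notes are a separate item.) There are two possibilities:
- The form is the same in both arms. A tourniquet score in one arm and a blank in the other then shows the arm.
- The item appears only on the LA-T form. The form then shows the arm, and the questionnaires are not identical.

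Either way, the arm is disclosed when that item is reached. Whether this comes before or after the primary VAS is not stated.

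**5. Scale.** The documents give no estimate of expectation bias. They do allow a calculation of how much would be needed to remove nominal significance, using the figures in SAP Section 9 and a t-based interval (the primary test is Mann–Whitney, so this is approximate):
- Difference: 2.08 − 0.80 = 1.28 VAS points.
- With the stated pooled SD of 1.52: SE = 1.52 × √(2/50) = 0.304; lower 95% limit = 1.28 − 1.984 × 0.304 = 0.68.
- With the SD implied by the stated d of 0.75: 1.28/0.75 = 1.71; SE = 1.71 × 0.2 = 0.341; lower 95% limit = 1.28 − 1.984 × 0.341 = 0.60.

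A bias of about 0.6 to 0.7 points in the between-arm difference would bring the lower limit to zero. This says nothing about whether a bias of that size occurred. That the stated SD and stated d disagree is a separate matter and does not affect this point.

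**The case against.** The best defence has four parts.

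*Patients may not have known what their experience meant.* A patient who feels a cuff need not know the arm's name, the alternative or the hypothesis. This stands in part: the consent text is not available, so what patients expected, and in which direction, cannot be checked. It does not restore patient blinding, because the patient still knows whether a cuff was inflated and no measure conceals it.

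*Higher pain under a cuff is real.* This stands. The secondary hypotheses in Section 3 expect tourniquet pain to raise intraoperative pain in LA-T. That pain is part of the treatment effect; the concern is only with reporting bias added to it.

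*The assessors are said to be blinded in Sections 4, 8, 11 and 12.* A reader might infer that the tourniquet item did unblind them for the primary outcome. The documents do not support that: with no item order given, the overall VAS may have been recorded first, and the assessor could have been blind at that moment. What can be said is that the plan does not show how blindness was kept.

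*The patient fills in the form too.* Section 12 has it completed by patient and assessor together. If the primary VAS was entered by the patient alone, the assessor's influence would be smaller, but the plan does not describe that.

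**Conclusion.** The point holds. Patient blinding is stated in Section 4, and implied by the double-blind label in Sections 2 and 4, but the design described does not have it. Assessor blinding is possible but not secured.

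The consequence is a risk of expectation bias of unknown size in the primary pain VAS and in satisfaction. The conclusion rests on patients being awake, on the absence of any described sham or concealment of the cuff, and on the tourniquet VAS being collected with the other VAS scores.

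Several stronger readings are tempting but not supported:
- That the trial is open-label throughout. Assessor blinding is unresolved, so that label could be wrong as well.
- That the two arms were certainly operated on in different rooms. The room for LA-T surgery is only inferred from injection there about 5 minutes before incision.
- That the bias must favour WALANT, or that some given share of the 1.28-point difference is artefact. The documents hold nothing from which to derive either.

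**What to change.** 1. In Sections 2 and 4, replace the double-blind label with: patients and surgeons not blinded; outcome assessors intended to be blinded. Correct the patient entry under Masking in Section 4 and the patient statement in Section 11 to match.
2. Do not present blinding as an advantage over earlier non-blinded studies.
3. State whether the tourniquet item was collected after the primary VAS and satisfaction. If it was not, report the assessor as unblinded for those outcomes.
4. List patient unblinding as a limitation on the primary and satisfaction conclusions, keeping expectation bias distinct from real cuff pain.
5. For any data still to be collected, record the primary VAS and satisfaction before any tourniquet question.

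Items 1 to 4 need only wording and one factual disclosure. Item 5 helps only if collection is still under way; the study period in Section 5 ends in December 2025 and the documents already quote results. No change to treatment is asked for. The cost is the loss of the double-blind label.

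### The only safety endpoint is labelled intraoperative with no stated start or end, so reactions to the earlier, out-of-theatre WALANT injection need not be counted

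*Combined protocol and SAP*

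**What the plan says.** Safety is specified in four places, always with the same label. The objective in Protocol Section 3 is "To describe intraoperative complications in each group". The outcome in Section 8 is "Intraoperative complications: bleeding requiring intervention, nerve injury, or other deviations from normal course". SAP 1 lists "Intraoperative complications (yes/no; type" among the secondary endpoints. SAP 6, item 5, gives counts and proportions by group, with a test only if there are enough events, and adds: "Given low expected event counts, analysis is primarily descriptive". None of these says when the window opens or closes.

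Section 7 separates the injections by content, time and place. WALANT receives "20 mL of 1% lidocaine (200 mg) with epinephrine 1:100,000", "Infiltrated into the operative field approximately 20 minutes before incision in a preoperative area". LA-T receives the same lidocaine dose without epinephrine, "Infiltrated approximately 5 minutes before incision in the operating room". The LA-T tourniquet comes down after the skin is closed.

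The risk list in Section 14 includes "allergic reaction, cardiovascular effects of epinephrine; these are standard risks of hand surgery and local anesthesia".

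Two passages are wider than the endpoint. Section 12 has the postoperative questionnaire capture complications without restricting them to surgery. Section 4 describes follow-up across the perioperative period up to an early postoperative assessment.

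**The concern.** The two drug-related risks named in Section 14 can begin at the injection, but the endpoint is named after the operation. Because the arms are injected at different times and in different rooms, an operation-based window leaves out a different stretch of post-injection time in each arm, and the longer stretch belongs to the only arm with epinephrine. A report that WALANT showed no excess of injection reactions could then come partly from the counting rule.

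The denominator is also exposed. SAP 2 admits randomized patients to the ITT set only if primary outcome data exist, SAP 8 makes the primary analysis complete-case, and no separate safety population is defined. A patient whose surgery is cancelled after a reaction has no intraoperative pain score and can leave the denominator as well as the numerator.

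**Working it through.** The documents give no figure for safety to reproduce; their post-hoc power concerns the pain score and has no bearing here. The check is a comparison of time windows.

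**Inputs.** Injection to incision: about 20 min (WALANT) and about 5 min (LA-T), Section 7. Patients per arm: 50, Section 9. The only operative interval defined anywhere runs from incision to the end of skin closure; Section 8 defines it for operative time, not for complications.

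**Post-injection time left out before the window, by reading**

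| Window opens at | WALANT, per patient | LA-T, per patient |
|---|---|---|
| Skin incision | about 20 min | about 5 min |
| Entry to operating or procedure room | up to about 20 min | 0 min |
| Injection (not stated in the endpoint) | 0 min | 0 min |

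The readings should not be mixed: on the incision clock LA-T also loses its 5 minutes, and only on the room-based reading does it lose nothing. On the incision clock the totals are 50 × 20 = 1,000 patient-minutes in WALANT and 50 × 5 = 250 in LA-T, a ratio of 4 to 1. This measures unobserved time, not risk, because the documents give no time course for reactions.

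**At the other end.** If the window also closes at skin closure, events at or after tourniquet release fall outside it. These can occur only in LA-T, so this omission works in LA-T's favour.

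**What a count in 50 patients can show.** Let *r* be the WALANT reaction rate and *f* the share of reactions that start and end before the window. Both are assumptions; neither is in the documents. The chance of recording at least one event is 1 − (1 − r(1 − f))^50.

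| Assumed r | f = 0 | f = 0.5 | f = 1 |
|---|---|---|---|
| 1% | 39% | 22% | 0% |
| 2% | 64% | 39% | 0% |
| 5% | 92% | 72% | 0% |
| 10% | 99% | 92% | 0% |

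A record of 0/50 has an exact two-sided 95% upper limit of 1 − 0.025^(1/50) = 7.1%, and that limit applies only to events inside the window. In the worst case, 3 reactions in 50 (6%, assumed), all over before the window and none counted, would be reported as 0/50.

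**The case against.** The strongest reply is that the exclusion is inferred. No passage says that a reaction before incision is not to be counted, and the incision-to-closure clock belongs to operative time. The questionnaire in Section 12 takes complications without qualification, Section 4 follows patients perioperatively, and the endpoint has a catch-all for other deviations. Much of this stands: a reader might infer that early reactions go unrecorded, and the documents do not support that. Some may be on the questionnaire, and any that persist past the start of the window would count. But the catch-all widens the type of event and not the time, and what is analysed still carries the intraoperative label. Nothing obliges a site to count an event in the preoperative area.

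A reader might also infer that the whole complications comparison is tilted toward WALANT. That is not supported either, because the possible loss of tourniquet-release events runs the other way.

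Finally, the consequence is limited. There is no safety hypothesis, the analysis is mainly descriptive, known allergy or contraindication to either drug and ASA III or higher are excluded, and the primary outcome is untouched. All of that is fair. But when the analysis is descriptive, the raw count is the result, and no model corrects an uneven count afterwards.

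**Conclusion.** The point holds for injection reactions. Under either natural reading of the label, the endpoint need not count reactions before the window, and the uncounted time is longer in WALANT: about 20 versus 5 minutes per patient from incision, up to about 20 versus 0 from room entry. It rests on the label and on the protocol's own description of where WALANT is injected, not on an express exclusion.

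Three things are not established: that early reactions were in fact lost, how many there might be, and the net direction of bias over all complications. The 3/50 example is an assumed worst case, not an estimate. The change is worth making because describing complications by group is a stated objective and the remedy is cheap; the primary analysis does not depend on it.

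**What to change.** In Protocol Section 8, SAP 1 and SAP 6 item 5, with the Section 3 objective and the Section 12 form worded to match:

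- Redefine the endpoint as perioperative complications, counted in both arms from first needle insertion, wherever it takes place, to the early postoperative assessment. This brings tourniquet release inside the window.
- List allergic reactions and cardiovascular reactions after injection as event types, beside bleeding and nerve injury.
- Report events by period: injection to incision, incision to closure, after closure.
- Use as denominator all patients who received a study injection, whether or not surgery was completed, and keep this safety set separate from the SAP 2 ITT set.

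The documents already quote observed results. If data collection is complete, apply the definition to the available records in both arms alike, or state that pre-incision events were not systematically captured and limit the safety conclusion accordingly.

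The cost is wording plus a small amount of extra recording or record review. WALANT may show a few more minor events. No dose, timing or clinical management changes.
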